5.2.2. Management of Reactogenicity and Other Adverse Events

Events following injection that may require clinical evaluation include a fever of 38.5°C/101.3°F (Grade 2) or higher lasting greater than 24 hours, rash, urticaria, or significant impairment in the activities of daily living (ADL). Fever of any severity or any condition which in the judgment of

the clinician should be evaluated would require a clinical visit. Participants are permitted to initiate an unscheduled clinic visit at their discretion but these visits will be compensated as per Section 11.5.

5.2.3. Management of Laboratory Abnormalities Following Vaccination

If the ALT, creatinine, hemoglobin and/or platelet count are Grade 3 or Grade 4, then repeat testing of the abnormal test will be performed within 48 hours. The specific timing of repeat testing for a Grade 2 laboratory test change will be determined by the study clinicians as medically appropriate.

5.3. Concomitant Medications

Current concomitant medications are recorded in the study database at enrollment and for 7 days post-vaccination. Subsequently, concomitant medications will be updated in the study database if there is an occurrence of an adverse event that is considered related to the IP or that requires expedited reporting or development of a new chronic medical condition that requires ongoing medical management.

Clinicians should discuss with study participants with regard to the timing of FDA-approved vaccines. Receipt of a licensed vaccine during study participation will be recorded in the study database. Otherwise, a record of concomitant medication changes throughout the study will not be recorded in the study database.

5.4. Study Discontinuation

The study may be stopped or cancelled at any time by decision of the PI, Walter Reed Army Institute of Research (WRAIR) IRB, the United States Army Medical Research and Materiel Command's (USAMRMC) Office of Research Protections (ORP), Human Research Protection Office (HRPO), NIAID, the U.S. FDA, U.S. DoD or the Office for Human Research Protection (OHRP).

5.5. Early Discontinuation or Withdrawal of Study Participants

A participant may be discontinued from protocol participation for the following reasons:

1. Repeated failure to comply with protocol requirements
2. Participant requests withdrawal
3. Participant develops a medical condition that is a contraindication to continuing study participation
4. The PI assesses that it is not in the best interest of the participant to continue participation in the study

Each participant has the right to withdraw from the study at any time for any reason without affecting the right to treatment by the investigator. The investigator should make an attempt to contact participants who did not return for scheduled visits or follow-up. Although the participant is not obliged to give reason(s) for withdrawing prematurely, the investigator should make a reasonable effort to ascertain the reason(s) while fully respecting the participant's rights.

Any participant who withdraws consent will not have any further data collected after consent has been withdrawn. However, samples and data that were collected prior to a participant's withdrawal of consent will be used/included in sample and data analysis.

The investigator also has the right to withdraw a participant, e.g., because of worsening health status, intercurrent illness, or other event, which makes further follow-up impossible.

As this is a phase I open label study, participants may be replaced if they did not receive the study injection. A volunteer who has been assessed as eligible for the study through screening will take the place of the participant that did not receive the study injection. The participant who did not receive the study injection will not count toward the total participants enrolled in the study.

5.6. Management of Participants Who Become Pregnant

Pregnant women and women who plan to become pregnant during the first 24 weeks after study vaccine administration are excluded from enrollment. If a participant becomes pregnant during the course of the study, they will continue to be followed for the remainder of the study period for safety. Blood draws will be conducted for safety purposes only. The PI or designated associate investigator will be responsible for reporting any pregnancy. New pregnancies will be reviewed weekly in aggregate with other safety data and forwarded as necessary to IRBs and study sponsors.

If a participant becomes pregnant within 24 weeks after the study vaccination, every effort will be made to remain in contact with the pregnant participant to record the outcome of pregnancy for the study database. Pregnancy outcomes will be recorded via a standardized pregnancy CRF. Information documented on this form will include date of last menstrual period, date pregnancy confirmed, history of complications during prior pregnancies (such as congenital abnormalities or spontaneous abortions). A separate pregnancy outcome CRF will be completed for the outcome of the pregnancy including date of termination or delivery, any complications of pregnancy, the gender, weight, presence of any congenital abnormalities, APGAR score, other complications of delivery and status of the child.

5.7. Management of Participants Who Become Incarcerated

Participation of prisoners is not planned and any participant will be suspended from study visits while incarcerated, except visits or telephone contact for the purpose of ensuring participant safety. No study product will be administered to a participant who is incarcerated. The IRB will be notified of the period of incarceration. Data and samples that were collected before the period of incarceration may still be stored and used for analyses. After release from incarceration, the participant may either return to participation in study visits according to the SOE or study participation may be terminated at the discretion of the PI.

Participants who have returned to the clinic after a period of incarceration will be counseled again about the potential risks of being a participant in the study. A note to the effect that the counseling was done will be written in the progress notes in the participant's binder.

Any participant who is incarcerated for more than 6 months will be re-consented to include taking and passing the AOU.

5.8. Management and Counseling of Participants with Positive HIV or Syphilis Test

Participants found to be infected with HIV or syphilis at screening will be counseled appropriately by a study physician, and then referred to their primary care physician or to a local free clinic. For civilian study participants, these new diagnoses of HIV or syphilis will be reported to the State of Maryland Public Health Department. In accordance with Maryland state law, all reportable diseases are reported to the Health Department, along with the participant's name, contact information, including address and telephone numbers, and the type of testing that was done on this participant. If the individual is an Active Duty service member, the participant's new diagnosis will be reported to the Preventive Medicine service at the Walter Reed National Military Medical Center for further counseling and referral to care within the Military Health System. As part of the informed consent process, participants will be informed that a positive HIV test or a positive syphilis test will prompt reporting, and that if the participant is Active Duty, their chain of command may be informed.

6.0 PHARMACY AND VACCINE ADMINISTRATION PROCEDURES

Study treatment is defined as VRC-MARADC087-00-VP (cAd3-Marburg). The study groups are shown in Table 1.

6.1. Study Product Formulation, Storage, and Preparation

6.1.1. Formulation

The recombinant chimpanzee adenovirus Type 3-vectored Marburg vaccine, VRC-MARADC087-00-VP (cAd3-Marburg) is composed of a cAd3 vector that expresses Marburg WT GP. The drug substance was manufactured by Advent S.r.l. (Pomezia, Italy, a subsidiary of Okarios, Inc.) and the vaccine, VRC-MARADC087-00-VP and diluent were manufactured at the VRC Pilot Plant (VPP) operated by the Vaccine Clinical Materials Program (VCMP), Leidos Biomedical Research, Inc., Frederick, MD (formerly SAIC-Frederick, MD), according to cGMP regulations. The drug product is a sterile, aqueous, buffered solution composed of cAd3 Marburg drug substance filled into single dose vials at 1×10^{11} PU/mL. Vials are aseptically filled under cGMP to a volume of >1.0 mL to allow withdrawal of 1.0 mL for IM administration. This monovalent vaccine will be tested at two doses, 1×10^{10} PU/mL and 1×10^{11} PU/mL. Additional details on VRC-MARADC087-00-VP composition and manufacturing can be found in the Investigator Brochure.

The diluent, VRC-DILADC065-00-VP, was manufactured at the VPP. It is comprised of the formulation buffer and will be used to dilute the cAd3-Marburg vaccine to prepare the 1×10^{10} PU/mL dosage to be administered in this study. The formulation buffer is pH 7.4 and consists of 10 mM Tris, 10 mM Histidine, 5% Sucrose (w/v), 75 mM Sodium Chloride, 1 mM Magnesium Chloride, 0.02% Polysorbate 80 (PS-80) (w/v), 0.1 mM EDTA, and 0.5% (v/v) Ethanol. The diluent is supplied in 3 mL glass vials at a fill volume >1.0 mL to allow withdrawal of 1.0 mL. Additional diluent VRC-DILADC065-00-VP composition and manufacturing information can be found in the Investigator Brochure.

6.1.2. Study Product Labels

The labels for the VRC-MARADC087-00-VP (cAd3-Marburg vaccine) and VRC-DILADC065-00-VP, diluent, will have specific product information (e.g., part number, lot number, fill volume, storage temperature) included on the product vial labels. The vaccine label will contain an Investigational Use Statement (“Caution: New Drug – Limited by Federal Law to Investigational Use”), and manufacturer information.

6.1.3. Study Product Storage

VRC-MARADC087-00-VP (cAd3-Marburg vaccine) will be stored at $\leq -60^{\circ}\text{C}$, and VRC-DILADC065-00-VP (cAd3 diluent) will be stored will be stored at -45°C to -10°C in a qualified, continuously monitored, temperature-controlled freezer.

If deviations in storage temperature occur from the normal allowance for the pharmacy freezer, the storage temperature excursion will be promptly reported to the PI and the IND sponsor. The excursion must be evaluated and investigated and action must be taken to restore and maintain the desired temperature limits. Following the outcome of the investigation, the IND sponsor will notify the pharmacist if continued clinical use of the product is acceptable.

6.1.4. Preparation of Study Product for Injection

This section describes how the site will prepare study injections. Clinician instructions on how to select an arm and administer the injection are in Section 5.2.

To prepare the vaccine for injection, the vials containing cAd3-Marburg and/or diluent will be thawed at ambient temperature (15-25°C).

Preparation will be done in a clean preparation unit with limited access. Only the required vials will be present in the preparation unit during dilution, and medication labels should be strictly segregated to avoid mix-ups. All injections will be administered IM into the deltoid muscle by needle and syringe and must be administered within 4 hours after removing the vaccine vial from the freezer.

Product dilutions will be prepared in a Class II biosafety cabinet.

Preparation of VRC-MARADC087-00-VP (cAd3-Marburg) at 1×10^{10} PU dose

Preparation of the 1×10^{10} PU dosage of cAd3-Marburg requires one serial dilution. Remove one vial of cAd3-Marburg vaccine and two vials of cAd3 diluent from the freezer and allow them to equilibrate to room temperature. Using 1 mL sterile syringes, draw up 1 mL of diluent from one diluent vial and 0.35 mL from the other diluent vial and inject these volumes into a 10 mL sterile vial. Then, using a 1 mL sterile syringe draw up 0.15 mL of the 1×10^{11} PU/mL vaccine and inject this into the 10 mL vial with the diluent to achieve a total volume of 1.5 mL. Vortex the vial at half speed for 3-5 seconds. This vial now contains 1.5×10^{10} PU VRC-MARADC087-00-VP in 1.5 mL and has a concentration of 1×10^{10} PU/mL. One 1 mL injection of this preparation will be administered for each dose. Discard remnant vaccine in vial in a biohazard container for incineration.

Preparation of VRC-MARADC087-00-VP (cAd3-Marburg) at 1×10^{11} PU dose

No dilution is needed for preparation of the 1×10^{11} PU dosage of cAd3-Marburg vaccine. Remove one vial of vaccine from the freezer and allow it to equilibrate to room temperature. Withdraw a total of 1 mL from the vial. One 1 mL injection of the preparation will be administered for each dose. Discard remnant vaccine in a vial in a biohazard container for incineration.

6.2. **Study Product Accountability**

6.2.1. Acquisition/Distribution

The study product(s) for this protocol are supplied by the Vaccine Research Center, NIH and should be obtained by following the instructions in the Manual of Procedures.

6.2.2. Documentation

The site will be responsible for maintaining an accurate record of the codes, inventory, and an accountability record of vaccine supplies for this study. Electronic documentation as well as paper copies will be used.

The VRC will receive copies of pharmacy records at the end of the study.

6.2.3. Disposition

The empty vials and the unused portion of a vial will be discarded in a biohazard containment bag and incinerated or autoclaved following the injection. Any unopened vials that remain at the end of the study will be destroyed at the discretion of the VRC in accordance with policies that apply to investigational agents. Partially used vials or expired prepared doses will not be administered to other participants nor used for *in vitro* experimental studies and will be discarded as indicated above.

7.0 PHARMACOVIGILANCE, SAFETY AND ADVERSE EVENT REPORTING

7.1. Definitions

Adverse Events

An adverse event (AE) is any untoward or unfavorable medical occurrence in a participant administered a pharmaceutical product and does not necessarily have a causal relationship with this product. An AE can therefore be any unfavorable and unintended sign (including an abnormal laboratory finding), symptom, or disease temporally associated with the use of a study product, whether or not considered related to the study product. (International Conference on Harmonization (ICH) E6) (Synonym: Adverse Experience).

Serious Adverse Events

As defined in 21 CFR 312.32, an adverse event or suspected adverse reaction is considered "serious" if, in the view of either the investigator or sponsor, it results in any of the following outcomes: "Death, a life-threatening adverse event, inpatient hospitalization or prolongation of existing hospitalization, a persistent or significant incapacity or substantial disruption of the ability to conduct normal life functions, or a congenital anomaly/birth defect. Important medical events that may not result in death, be life-threatening, or require hospitalization may be considered serious when, based upon appropriate medical judgment, they may jeopardize the participant and may require medical or surgical intervention to prevent one of the outcomes listed in this definition. Examples of such medical events include allergic bronchospasm requiring intensive treatment in an emergency room or at home, blood dyscrasias or convulsions that do not result in inpatient hospitalization, or the development of drug dependency or drug abuse."

"Life-threatening" refers to an adverse event that at occurrence represents an immediate risk of death to the participant; it does not refer to an event that hypothetically might have caused death if it were more severe. Similarly, a hospital admission for an elective procedure is not considered an SAE.

All AEs will have their possible relationship to study vaccine assessed and will be graded according to the table for grading severity of adverse events (see Appendix 9). Arthralgia (joint pain) and arthritis AEs will be graded in accordance with the criteria in Appendix 10.

7.2. Adverse Event Grading and Recording

Recording of all AEs will occur during the period from study agent administration through 28 days after study agent administration. Solicited AEs will be recorded in the study database for 7 days after injection without the collection of attribution to study vaccine. All unsolicited AEs and SAEs that occur during the period from study agent administration through 28 days after study agent administration will be recorded in the study database. After study day 28, only SAEs and new chronic medical conditions that require ongoing medical management will be recorded as AEs in the study database. Because this is a Marburg vaccine study, in the extremely unlikely circumstance of Marburg diagnosis in a study participant at any time throughout the study, this will be recorded on a "Marburg CRF", rather than an AE form, without requiring an investigator attribution ("relatedness to study agent") or severity grade.

The FDA Guidance for Industry (September 2007): "Toxicity Grading Scale for Healthy Adult and Adolescent Volunteers Enrolled in Preventive Vaccine Clinical Trials" was adapted for the severity grading of adverse events in this protocol. The FDA Guidance of Industry on toxicity

grading scale is modified for criteria on absolute neutrophil counts and other parameters as described in Appendix 9, which also includes the definitions for severity grading parameters that do not have specific guidelines in the table. Due to the absence of specific grading criteria for arthralgias on the FDA toxicity grading scale, the “DAIDS AE Grading Table Corrected” (Version 2.1-July 2017) (Appendix 10) will be used to grade arthralgia AEs.

The clinical investigators will monitor and analyze study data including all AE and lab data as they become available and will make determinations regarding the severity of the adverse experiences and their relation to study product. AE CRFs will be completed by the research staff on a daily basis as the data become available from the clinic or laboratory. AEs are also subjected to analysis to identify those that may invoke study pause rules. Although post injection reactogenicity (PIR)/Solicited AEs are documented separately from unsolicited AEs, they will be reported if they meet SAE or study pause rule definitions as noted below. Therefore the PI or designee must review both PIR and AE CRFs to ensure prompt and complete identification of all events that require expedited reporting as SAEs, study pause rules or other serious and unexpected events.

AEs will be followed by the clinical research team until resolved, and stability or chronicity has been established and documented.

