Participants will be given a “Diary Card”, a thermometer, and a ruler. The diary card will be used as a memory aid, on which the participant will record temperature, local and systemic symptoms and concomitant medications daily for 7 days after the injection. Participants will be trained to complete the paper diary card, how to use the thermometer, and how to measure injection site swelling and redness using the ruler. Completion of the diary card training will be noted in source documents. The written (paper) diary card will be transcribed into the study database and will be stored in the participant file for monitoring purposes.

The solicited signs and symptoms on the diary card (among others) will include: joint pain, unusually tired, muscles aches (other than at injection site), headache, chills, nausea, and pain at injection site. Participants will also record the day’s highest measured temperature and measurement of largest diameter for redness and swelling at the injection site. The completed diary cards are collected at the first visit following completion of the 7-day diary card (about 2 weeks after the injection).

Follow-up on participant well-being will be performed by telephone or clinic visit on the day following vaccination and by clinic visit on Day 3 following the injection to assess their clinical status. Participants may call or come to the clinic at any time-point for evaluation, if they experience unusual, moderate or severe signs and symptoms. Diary cards will be reviewed with the clinician at any visit from day of vaccination through the first study visit following completion of the diary card. If upon reviewing the clinician finds that general symptom or injection site symptom information (except swelling or redness measurements) is missing from the diary cards, the participant will be asked to provide the missing information to the best of their recollection.

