7.4. Criteria for Study Pause or Termination

The Principal Investigator will closely monitor and analyze study data as they become available and will make determinations regarding the presence and severity of adverse events. The administration of study injections and new enrollments will be paused and the IND Sponsor will be promptly notified according to the following criteria:

- **One** (or more) participant experiences a **SAE** that is assessed as possibly, probably or definitely related to study agent, or
- **Two** (or more) participants experience the same **Grade 3 or 4** adverse event assessed as possibly, probably or definitely related to study agent.

Plan for Review of Pauses and Resuming Rules:

The study injections and enrollments would resume only if review of the adverse events that caused the pause resulted in a recommendation to permit further study injections and study enrollments. The reviews to make this decision will occur as follows:

Pauses for SAEs: The IND Sponsor and PSRT will conduct the review, consult with the FDA, if needed, and make the decision to resume, amend or close the study for any SAEs that meet the criteria for pausing the study. The FDA will be notified of any SAE pause review.

Pauses for Grade 3 or 4 AEs: The IND Sponsor and PSRT will conduct the review and make the decision to resume, amend or close the study for the Grade 3 or 4 events that meet the criteria for pausing the study. As part of the pause review, the reviewers will also advise on whether the study needs to be paused again for any subsequent Grade 3 or 4 event of the same type. The FDA will be notified of all Grade 3/4 pause reviews.

When indicated, safety data reports and changes in study status (study pauses) will be submitted to the IRB in accordance with Section 12.2 and institutional policy.

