8.3.4. Interim analyses

Safety Reviews: The PSRT will review safety data routinely throughout the study. The study will utilize both electronic database features and reviews by designated safety review personnel to identify in a timely manner if any of the safety pause rules of the study are met.

Immunogenicity Review: Periodic analyses of immunogenicity for each group may be performed during the study for the purpose of informing future vaccine-related decisions in a timely manner once there are at least 3 participants in the group with the 4 weeks post vaccination follow-up completed. The results will not influence the conduct of the trial in terms of early termination or later safety or immunogenicity endpoint assessments.

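### Can the Grade 3/4 pause rule work when the study database holds no attribution for solicited reactions?

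*Combined protocol and SAP*

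**What the plan says.** Section 7.4 sets two pause criteria. The one at issue needs two or more participants with the same Grade 3 or 4 "adverse event assessed as possibly, probably or definitely related to study agent".

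Section 7.2 brings solicited reactions under that rule. They are documented apart from unsolicited events, but "they will be reported if they meet SAE or study pause rule definitions as noted below". It then assigns the task of finding them: "Therefore the PI or designee must review both PIR and AE CRFs to ensure prompt and complete identification of all events".

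The same section limits what the database holds: "Solicited AEs will be recorded in the study database for 7 days after injection without the collection of attribution to study vaccine".

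Section 7.1 makes no exception for solicited events: "All AEs will have their possible relationship to study vaccine assessed and will be graded".

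Section 8.3.4 describes how pause events are detected: "The study will utilize both electronic database features and reviews by designated safety review personnel to identify in a timely manner".

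Section 5.2.1 lists the solicited symptoms on the diary card, among them "joint pain, unusually tired, muscles aches (other than at injection site), headache, chills, nausea, and pain at injection site", together with temperature, redness and swelling. It says of the card: "The written (paper) diary card will be transcribed into the study database and will be stored in the participant file for monitoring purposes".

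**The concern.** The pause criterion has three elements: grade, a count of participants with the same event, and relatedness. For solicited reactions in the first seven days the database can supply the first two but not the third. If the electronic check in Section 8.3.4 were the only safeguard, it could not test the rule as written.

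The timing makes this look worse. Section 1.2 says this vaccine has not been given to humans before. Section 11.3.1 says systemic reactions typically come on the day of vaccination or the day after, inside the window without attribution. The reviews that release the next stage of enrollment (Section 7.3) can take place once follow-up reaches the Day 7 visit, so they draw heavily on the same data.

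There is also an asymmetry in the record. A pause produces notices to the sponsor, the FDA and the IRB (Sections 7.4, 7.5.4 and 12.4). A judgement of unrelated that keeps the count below two produces none, and no section says where it is written down. With exactly two affected participants, one such judgement decides whether the criterion is met.

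**Working it through.** The plan gives no operating characteristics for its pause rule, so there is no stated figure to reproduce. The check has three parts.

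**1. Do the sections conflict?**

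| Question | Where answered | Answer for a solicited reaction in days 0 to 7 |
|---|---|---|
| Is relatedness assessed? | 7.1; 7.2 (investigators determine severity and relation to product) | Yes |
| Is it collected in the study database? | 7.2 | No |
| Does the pause rule apply? | 7.2 | Yes |
| Who looks for pause events? | 7.2 | PI or designee, from the reactogenicity and adverse event forms |
| Is detection left to the database? | 8.3.4 | No; database features plus safety reviewers |
| Where is the judgement filed? | No section | Not stated |

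Section 7.1 concerns assessment and the sentence in Section 7.2 concerns database capture, so both can be followed. Section 8.3.4 does not promise that the electronic part tests every element. The database can flag grade and count, and a person supplies relatedness. Only the last row is open.

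**2. How many records are involved?**

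- Diary card items (Section 5.2.1, Appendix 13): 6 general symptoms + local pain + swelling + redness + temperature = 10.
- Participants (Section 4.0): 40.
- Section 8.3.2 counts each participant once per sign, at maximum severity: 10 × 40 = 400 records.

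Only Grade 3 or 4 records bear on the rule, and the documents give no rate for them. Under assumed shares:

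- 1%: 0.01 × 400 = 4 records
- 2.5%: 0.025 × 400 = 10 records
- 5%: 0.05 × 400 = 20 records

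These figures are the number of entries an added field would receive. They do not measure harm.

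**3. Would recording the judgement change the rule's behaviour?**

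Let p be the true rate of one particular Grade 3/4 solicited reaction and s the share of such reactions judged unrelated, both assumed. Each participant counts toward the rule with probability q = p(1 − s). In a group of 20,

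P(at least 2 count) = 1 − (1 − q)^20 − 20q(1 − q)^19.

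With p = 10%:

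| s | q | P(at least 2 of 20 count) |
|---|---|---|
| 0 | 0.100 | 0.608 |
| 0.25 | 0.075 | 0.449 |
| 0.50 | 0.050 | 0.264 |

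For s = 0 this is 1 − 0.1216 − 0.2702 = 0.608. For s = 0.50 it is 1 − 0.3585 − 0.3774 = 0.264.

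The judgement clearly matters. But p and s are the only inputs at a given group size, and writing the judgement into the database alters neither. For any p and s, the probability with the field minus the probability without it is 0.

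**The case for a change.** The strongest case for a change is that a first-in-human safety rule should be auditable from the data, and that the remedy is cheap: one sentence and one conditional field. Section 8.3.2 carries relationship to treatment in the adverse event tables and listing but tabulates reactogenicity only by group and severity, so the gap runs through to reporting. Section 7.3 provides expedited review for serious events that may meet pause criteria and has no matching sentence for non-serious Grade 3 or 4 events. If solicited reactions are meant to count as related by default, no section says so.

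The textual points are correct: no supplied section names the place of record. The practical exposure is smaller than it sounds, for four reasons.

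- Two matching severe reactions are visible by grade whatever the PI decides on cause. The safety review team reviews all adverse events and sees aggregate data weekly until four weeks after the last vaccination. Its quorum includes the IND Medical Officer (Section 7.3), to whom all adverse events are reported (Appendix 12).
- The DoD Research Monitor must give input to the team by email when absent from its call (Section 7.3) and can stop the protocol independently (Appendix 12).
- Appendix 9 counts an event as possibly related even when other causes explain it equally well, so judgements of unrelated soon after injection should be uncommon.
- Source documents must support the database (Section 9.3), and monitors may inspect case report forms and clinical records (Section 13.2).

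The blank on the diary card proves little, since participants would not be asked to attribute cause. The investigator's reactogenicity form named in Section 7.2 is not among the documents and may hold the judgement.

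**Conclusion.** No change to the plan is needed. The rule can operate as written: investigators assess relatedness, the PI or a designee reviews the reactogenicity forms against the pause criteria, and the safety review team and the IND Medical Officer see the same events. Leaving attribution out of the database is compatible with assessing it.

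The open detail is where a judgement of unrelated is filed for a non-serious Grade 3 or 4 solicited reaction confined to days 0 to 7. Serious events, unsolicited events and symptoms lasting beyond Day 7 (Section 5.2.1) fall outside it. Settling it would add perhaps 4 to 20 entries under the assumed 1% to 5% shares, with no change in the pause probability and no trial estimate altered. It is a records question that study staff can answer from the case report form and source notes.

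This conclusion assumes that investigators make the assessment Section 7.1 requires. It rests on the protocol text alone, because the reactogenicity form and the Manual of Procedures were not supplied. It takes no position on the pause threshold.
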